Indicate which of the following populations will be included in this research

- ✓ Adults over 50

Research Support/Funding

Will an existing internal account be used to support the project?

Yes

Describe internal account

[name] University Irving Scholar account

Is the project externally funded or is external funding planned?

No

Study Location

Indicate if the research is/will be conducted at any of the following

✓ NYSPI

This protocol describes research conducted by the PI at other facilities/locations

No

Lay Summary of Proposed Research

Lay Summary of Proposed Research

In our ongoing studies of Posttraumatic Stress Disorder (PTSD) in older adults, we have found that older adults with PTSD frequently meet criteria for comorbid Major Depressive Disorder (MDD). Moreover, relative to trauma-exposed healthy controls (TEHCs), elders with PTSD manifest executive function deficits, fatigability, and mobility and physical function deficits that are consistent with what we have observed in depressed older adults. Yet, we have found that very few older adults with combined PTSD/MDD have received appropriate antidepressant treatment for their condition.

These findings give rise to the questions of (1) how effective is antidepressant treatment for depressive symptoms in the context of PTSD/MDD and (2) are cognitive and physical function deficits in PTSD/MDD patients reversible with effective antidepressant treatment?

Participants who recently completed IRB 7489 and who sign consent to participate in this open treatment study will be treated for 8-weeks with antidepressant medication. Participants will be seen in person for the week 0 (baseline) visit, where they will complete baseline testing. Participants will meet with research assistants and clinicians every two weeks virtually, via a HIPAA compliant video platform, Webex. They will then come in person for the final study visit, week 8. Week 8 will be conducted in person and will consist of repeat baseline testing. This will be the second study visit conducted in person, unless a significant clinical worsening occurs and/or the participant wishes to be seen in person for a visit. Following the 8 weeks, participants will be eligible for 3 months post protocol open treatment and will continue to receive referrals for PTSD treatment.

Background, Significance and Rationale

Background, Significance and Rationale

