In our ongoing IRB #7489, we hypothesize that chronic PTSD, over and above other contributing factors, accelerates biological aging in the brain and body, leading to adverse behavioral consequences such as frailty and cognitive decline. To test these hypotheses, 150 individuals are being recruited who are aged ≥ 50 and diagnosed with PTSD. A control group of 150 age-, sex-, and trauma exposure-matched subjects without PTSD are being recruited and assessed. Included subjects undergo comprehensive neuropsychological assessment and cerebral blood volume functional magnetic resonance imaging (CBV-fMRI) to assess regional hippocampal metabolic activity and function. Structural MRI is performed to quantify WMH, regional brain volume, and cortical thickness, while resting state fMRI measures functional connectivity within hippocampal networks. PTSD subjects and controls are compared on measures of aging within the following domains: neural (DG CBV, WMH, morphology), cognitive (processing speed, memory, executive function, pattern separation), somatic (peripheral inflammatory markers, leukocyte telomere length, and measures of oxidative stress), and behavioral (grip strength, gait speed, fatigue levels). By elucidating the interaction of chronic PTSD with aging processes, data from this project may contribute to the development of rationally designed, personalized, and age-appropriate novel treatments.

Interim analyses of PTSD subjects in this study demonstrate a high degree of comorbidity with MDD. Among participants with PTSD enrolled to date, 67.1% meet criteria for MDD and mean Hamilton Rating Scale for Depression (HRSD) is 18.1. The most prominent cognitive differences observed to date in our study between PTSD and TEHC subjects is executive dysfunction, which is common in late life depression. PTSD subjects have dramatically increased fatigability and prevalence of frailty criteria compared to TEHCs, abnormalities which are also frequently seen in our older MDD samples. Yet, we have found that less than 25% of these individuals are currently receiving an adequate dose and duration of first-line pharmacotherapy for MDD, while only one third report any past medication treatment. These data raise the question of whether patients with combined PTSD/MDD could benefit from adequate antidepressant medication treatment and to what degree their cognitive and physical function deficits would be reversible with this therapy.

Specific Aims and Hypotheses

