Specific Aims and Hypotheses

Aim 1. To study the effectiveness of antidepressant medications to treat depressive symptoms in older adults with PTSD/MDD.

Hyp 1: A significant improvement in depressive symptoms will be observed, and response rates to open antidepressant medication treatment in this population will be greater than 50%.

Aim 2: To evaluate change in cognition and physical function following antidepressant medication treatment.

Hyp 2: As compared to non-responders, responders to antidepressant treatment will demonstrate significantly greater improvement in executive function (NIH Toolbox) and gait speed.

Description of Subject Population

Sample #1

Specify subject population

Participants in IRB 7489 with combined PTSD and MDD

Number of completers required to accomplish study aims

20

Projected number of subjects who will be enrolled to obtain required number of completers

25

Age range of subject population

50 years and older

Gender, Racial and Ethnic Breakdown

We anticipate the sample will be composed of approximately 60% women and 40% men.

Racial/ethnic group: On the basis of previous depression studies conducted in the Clinic for Aging, Anxiety, and Mood Disorders, it is anticipated that the sample will be composed of approximately 75% Caucasian, 15% African American, and 10% Hispanic subjects.

Description of subject population

The proposed study will enroll 25 outpatients who are (1) participants in IRB 7489, (2) diagnosed with DSM 5 MDD, (3) have HRSD ≥ 18 , and (4) are willing to and capable of providing informed consent and complying with study procedures. Participants will be excluded for (1) history of allergic or adverse reaction to escitalopram and duloxetine, (2) non-response to adequate trial of escitalopram (at least 4 weeks at dose of 20mg) and duloxetine (at least 4 weeks at dose of 60mg) during the current episode, or (3) current treatment with psychotherapy, antidepressants, or other psychotropic medications.

Recruitment Procedures

Describe settings where recruitment will occur

Subjects will be recruited from participation in IRB 7489.

How and by whom will subjects be approached and/or recruited?

The research assistant will notify a study clinician once a participant completing IRB 7489 is known to meet the selection criteria. The clinician will then approach the participant and discuss potential treatment in this protocol, with its attendant risks, benefits, and alternatives.

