4. At Week 8 study endpoint, participants will return to the Clinic on Aging, Anxiety, and Mood Disorders (CAAM) and the Anxiety Disorders Clinic (ADC) for HRSD, HARS, CGI Severity and Improvement, PCL-5, and CAPS-5. In addition, repeat neuropsychological testing and physical function assessment (the same tests from baseline in IRB 7489) will be performed. These include frailty characteristics assessed from the Fried model: unintentional weight loss (10 lbs or 5% of body weight in the past year), self-reported exhaustion, weakness (grip strength), slow walking speed, and low physical activity. Exhaustion will be dichotomized as yes/no using a physical fatigability cutoff score of >10 on the Pittsburgh Fatigability Scale (PFS). Grip Strength is measured using a Jamar dynamometer with maximum grip strength measured over 3 trials. Gait will be assessed as walking speed in m/s on a GaitRITE walkway. Physical activity is assessed via a measure of weekly kilocalories (kcal) derived from the 18-item Minnesota Leisure Time Physical Activity Questionnaire. Function will be assessed using the Short Physical Performance Battery (SPPB), the 36-item self-report World Health Organization Disability Assessment Schedule 2.0 (WHODAS2), and the self-report Measure of Everyday Cognition (ECog). Cognitive scales will include Coding from WAIS-III, Trail Making Test Part A, Pattern and Letter Comparison Tests, Rey AVLT, in addition to testing with the NIH Toolbox for cognition supplemented by NIH EXAMINER.

5. As in IRB 7489, throughout all assessment procedures, the following safety plan will be in place to mitigate the risk that subjects will become frustrated or upset. First, a discussion will be had with participants as to the schedule of assessments. Flexibility will be maintained insofar as possible, such that assessments will be scheduled according to subjects' preferences (e.g., all at one time vs. breaking up over multiple sessions). Second, subjects will be offered a 15 minute break after each hour of assessments. Third, subjects will be informed that a study clinician is available should they become frustrated or upset. Upon the subject's request or if the subject appears upset, the research staff member conducting the assessment will stop the assessment and contact the study clinician. The study clinician will come assess the subject and make a determination of whether or not assessment may proceed or whether clinical treatment is indicated.

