Antidepressant Response in Older Adults
with Comorbid PTSD and MDD

Protocol ID 8111
NCT04697693

Statistical Analysis Plan

Document Version Date: January 29th, 2021

Statistical Analysis

Descriptive statistics for the sample at baseline will be computed and reported in terms of means with standard deviations. The hypotheses under investigation are that (1) individuals with comorbid PTSD and MDD will experience significant depressive symptom improvement with antidepressant treatment and that (2) cognitive and physical functioning will likewise significantly improve following antidepressant treatment. To investigate these hypotheses, paired samples t-tests will be used to analyze the within-subject change from pre- to post-treatment on depressive symptom severity (Hamilton Rating Scale for Depression [HRSD]), cognitive functioning (NIH Toolbox total score), and physical functioning (gait speed).

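### The SAP tests cognition against zero change on a battery already taken in IRB 7489, does not say which assessment is baseline, and so cannot separate retest gain from a treatment effect

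*SAP*

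**What the plan says.** The SAP's single Statistical Analysis section holds the whole plan for cognition: "paired samples t-tests will be used to analyze the within-subject change from pre- to post-treatment", with the NIH Toolbox total score as the cognitive outcome and gait speed as the physical one. The hypothesis tested is that "cognitive and physical functioning will likewise significantly improve following antidepressant treatment". The SAP has no comparator, alternate test form, allowance for retesting or caveat on interpretation, and it does not say which assessment supplies the pre-treatment value.

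In the protocol, Study Procedures item 4 says that at Week 8 "repeat neuropsychological testing and physical function assessment (the same tests from baseline in IRB 7489) will be performed", and the tests it lists include the NIH Toolbox. The Lay Summary says: "Participants will be seen in person for the week 0 (baseline) visit, where they will complete baseline testing".

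The purpose is put in causal terms. The Lay Summary asks: "are cognitive and physical function deficits in PTSD/MDD patients reversible with effective antidepressant treatment". The Background asks "to what degree their cognitive and physical function deficits would be reversible with this therapy". Hypothesis 2 in the protocol is comparative: "As compared to non-responders, responders to antidepressant treatment will demonstrate significantly greater improvement in executive function (NIH Toolbox) and gait speed". The SAP does not carry that comparison over.

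**The concern.** A paired t-test asks whether mean change differs from zero. On a cognitive battery taken for at least the second time, zero is not the change to expect without treatment, because people tend to do better on tasks they have seen before. With one arm and no adjustment, a retest gain and a drug effect look the same in this analysis.

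The protocol asks whether deficits reverse with treatment. A significant paired test invites the answer yes, and that answer could rest on practice alone. The undefined baseline adds to the problem. If the pre-treatment score is the IRB 7489 one, the change also spans a period before treatment whose length is not given; Concurrent Research Studies says only that IRB 7489 was completed recently.

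**Working it through.** **The plan's own figure.** Description of Subject Population gives 20 completers from 25 enrolled, which implies 20% loss (25 × 0.80 = 20). No alpha, power, effect size or SD is stated, so the 20 itself cannot be derived. It is the right n here, because participants who leave the study have no further research measures.

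**Assumptions, since the documents are silent.** Two-sided 5% test; no drug effect; retest gain g of 0.1, 0.2 or 0.3 baseline SD; retest correlation r of 0.7, 0.8 or 0.9; equal variances.

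**Chance that retest gain alone is significant.**
- SD of change = √(2(1 − r)) baseline SD.
- Noncentrality = g ÷ (SD of change) × √20, with 19 df and critical value 2.093.
- Example, r = 0.8 and g = 0.3: 0.3 ÷ 0.632 = 0.474; × 4.472 = 2.121; upper-tail rejection probability 52%.

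| r | SD of change | g = 0.1 | g = 0.2 | g = 0.3 |
|---|---|---|---|---|
| 0.7 | 0.775 | 8% | 19% | 38% |
| 0.8 | 0.632 | 10% | 27% | 52% |
| 0.9 | 0.447 | 16% | 48% | 81% |

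With g = 0 the figure is 2.5%. An observed mean change of 2.093 ÷ √20 = 0.468 SD of the change scores is enough for significance. At r = 0.8 that is 0.468 × 0.632 = 0.30 baseline SD.

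**Is the battery given at Week 0?**
- *For:* the Lay Summary places baseline testing at Week 0 and describes Week 8 as a repeat of it.
- *Against:* Study Procedures items 1 to 4 list no cognitive battery at Week 0, and item 4 takes the IRB 7489 baseline as the reference. Compensation pays Week 0 at the $25 rate of the biweekly visits and Week 8 at $100 for its assessments. Under Assessment Instruments, NIH-EXAMINER (1 hour) and the NIH Toolbox (45 minutes) alone take 1 hour 45 minutes.

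Week 0 testing is probable on the Lay Summary's wording but not established.

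**What a run-in contrast would cost.** If all three scores exist, (Week 8 − Week 0) − (Week 0 − IRB 7489) removes a retest gain that is equal in both intervals.
- Its SD is √(6(1 − r)), which is √3 times that of the paired change.
- The 95% CI half-width, 2.093 × SD ÷ √20, is 0.63, 0.51 and 0.36 baseline SD at r = 0.7, 0.8 and 0.9, against 0.36, 0.30 and 0.21 for the paired change.
- Power for a true 0.3 SD drug effect (noncentrality 1.00, 1.22, 1.73) is 16%, 21% and 38%, against 38%, 52% and 81% for the paired test when there is no retest gain.
- If practice gain halves, from 0.3 on the first retest to 0.15 on the second, the contrast is biased by −0.15. Power falls to 7%, 8% and 13%, and false improvement to below 1%.

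**Responder contrast.** With an assumed 10 to 10 split (18 df, critical value 2.101), the half-width is 2.101 × SD of change × √(1/10 + 1/10) = 0.73, 0.59 and 0.42 baseline SD. A retest gain common to both groups cancels.

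**The case against.** The strongest reply is that this is a declared open, single-arm study. Aim 2 is to evaluate change following medication, and a paired estimate does that. The SAP uses the same temporal wording and sets no rule for attributing change to the drug. That stands: it would be wrong to infer that the SAP formally reads any gain as benefit, or that the paired change leaves Aim 2 unanswered. What remains is that the documents pose the reversibility question twice, and the only cognitive test planned is against zero, with no caveat.

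A reader might also infer that the design already holds an untreated control interval, from IRB 7489 to Week 0, that merely goes unused. The documents do not establish this. The Week 0 battery is uncertain. Exclusion 3 covers current treatment at entry, not the whole interval. The Background reports that fewer than 25% of PTSD participants in IRB 7489, not none, were on adequate antidepressant treatment, and Study Procedures item 1 admits people who did not respond to or tolerate escitalopram in the current episode. Treatment may therefore have been taken or stopped within that interval.

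Making the run-in contrast a condition for claiming benefit would go too far, given its power of 16% to 38%. Finally, the practice argument concerns cognitive tests. Nothing in the documents supports extending it to walking speed on a GaitRITE walkway.

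**Conclusion.** The concern holds for the NIH Toolbox score. As the SAP stands, retest gain alone would produce a significant improvement in 8% to 81% of trials, against 2.5% nominal. That range rests wholly on the assumed gain (0.1 to 0.3 SD) and retest correlation (0.7 to 0.9) with 20 completers; the documents supply neither value. That the battery has been taken before needs no assumption, because the protocol says so.

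The unnamed baseline is a separate, documented gap and needs correcting on either reading of Week 0. Three administrations, a clean untreated interval and a matching problem for gait speed are not supported. The change is worth making: it costs little and alters what the trial can conclude about cognition.

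**What to change.** In the SAP:

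1. Name the pre-treatment assessment: the Week 0 battery if it is given, otherwise the IRB 7489 battery. Reconcile the Lay Summary, Study Procedures and Compensation sections on this point, and report the time between the two tests.
2. Report the paired NIH Toolbox change with its 95% CI as *change on retesting during open treatment*, not as a treatment effect. If IRB 7489 supplies the baseline, say that the interval starts before treatment.
3. Where IRB 7489 and Week 0 scores both exist and the participant took no antidepressant, other psychotropic or psychotherapy in between, add the treated-interval minus untreated-interval change with its 95% CI. Make it a supportive estimate, not a condition for success.
4. Restore the responder versus non-responder contrast of protocol Hypothesis 2, on the executive function outcome named there, as a non-randomised estimate with its 95% CI. State the definition of response, which neither document gives.

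The cost is SAP wording and the use of parent-study scores, with no added visit or test. The downside is precision: with 20 completers both contrasts have wide intervals. The run-in contrast over-corrects if practice gain shrinks on later exposures. The responder contrast removes only a gain that is the same in both groups.

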Hamilton Anxiety Rating Scale (HARS) 14-item scale: standard measure of anxiety severity in pharmacotherapy studies and has been shown to have good reliability and validity.

--15 minutes

24-item Hamilton Rating Scale for Depression (HRSD): standard measure of depression severity used across diverse patient samples, including PTSD.

--15 minutes

CGI Severity and Improvement: scales measuring the clinician's view of subjects' global functioning.

--1 minute

Digit Symbol test from the WAIS-III: measure of processing speed.

--2 minutes

Pattern and Letter Comparison tests: reliable measures of processing speed.

--4 minutes

Trail Making Test Part A: reliable test of motor speed.

--3 minutes

Selective Reminding Test: test of episodic memory functioning will allow us to identify deficits in episodic memory functioning consistent with a classification of amnesic mild cognitive impairment (aMCI).

--10-15 minutes

NIH-EXAMINER battery: designed to assess executive functions reliably, comprehensively, and efficiently. This battery examines working memory, inhibition, set shifting, fluency, insight, planning, social cognition and behavior.

--1 hour

NIH Toolbox Cognition Battery: brief, diverse, accessible, and psychometrically sound set of 7 computerized instruments that measure 6 ability subdomains important for cognitive health.

--45 minutes

Frailty characteristics: unintentional weight loss (10 lbs or 5% of body weight in the past year), self-reported exhaustion, weakness (grip strength), slow walking speed, and low physical activity.

--10 minutes

Pittsburgh Fatigability Scale (PFS): the only self-report measure of fatigability associated with performance and perceived exertion.

--5 minutes

Minnesota Leisure Time Physical Activity Questionnaire: measure of physical activities, with activity levels < 383 kcal considered frail.

--5 minutes

Posttraumatic Stress Disorder Checklist (PCL-5): 20-item self-report PTSD symptom screening instrument that has been shown to have good internal consistency, strong correlations with other PTSD scales, and high diagnostic efficiency.

--5-10 minutes

Clinician-Administered PTSD Scale for DSM-5 (CAPS-5): The CAPS is a 30-item instrument containing 0- 4 Likert-style item frequency and intensity scales for PTSD symptoms, with subscales for intrusion, avoidance, and hyperarousal symptom clusters, and associated affective features.

--45 minutes

Please attach copies, unless standard instruments are used

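### The protocol's cognitive hypothesis concerns NIH Toolbox executive function, but the SAP analyses only the Toolbox total score, so Hyp 2 is not tested as stated

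*SAP*

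**What the plan says.** Under Specific Aims and Hypotheses, the protocol states Aim 2 broadly: "To evaluate change in cognition and physical function following antidepressant medication treatment". Hyp 2 beneath it is narrower: "As compared to non-responders, responders to antidepressant treatment will demonstrate significantly greater improvement in executive function (NIH Toolbox) and gait speed". Executive function is the only cognitive measure it names.

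The SAP's Statistical Analysis section, the only analysis text in the two documents, states its second hypothesis as "cognitive and physical functioning will likewise significantly improve following antidepressant treatment". Its cognitive outcome is "cognitive functioning (NIH Toolbox total score"), and its method is that "paired samples t-tests will be used to analyze the within-subject change from pre- to post-treatment". It lists no executive-function score, from either the Toolbox or NIH-EXAMINER.

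The protocol's Assessment Instruments section describes the Toolbox battery as a "set of 7 computerized instruments that measure 6 ability subdomains important for cognitive health". It does not name the instruments or subdomains, and it does not say which of them would form an executive-function score.

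**The concern.** A total over several cognitive domains and a score for one of those domains answer different questions. A change confined to executive function can be diluted in the total and missed. A change in the total can come from other domains and say nothing about Hyp 2. Because the Toolbox yields both kinds of score and neither is tied to Hyp 2 in the SAP, the choice could also be made after the results are seen.

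Executive function does not look like an incidental word in Hyp 2. The Background section reports from the parent study that "The most prominent cognitive differences observed to date in our study between PTSD and TEHC subjects is executive dysfunction". That is consistent with choosing it as the target, although the protocol does not say that this is why it was chosen.

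**Working it through.** **Comparing the texts.** The finding rests on this comparison and on no number.

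| Element | Protocol Hyp 2 | SAP |
|---|---|---|
| Cognitive measure | Toolbox executive function | Toolbox total score |
| Physical measure | Gait speed | Gait speed |
| Contrast | Responders vs non-responders | Pre vs post, whole sample |

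The physical measure agrees. The cognitive measure and the contrast do not. Two separate repairs are therefore needed: changing the score alone would leave the contrast missing, and restoring the contrast alone would leave the wrong score.

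**How much of the total could be executive function.** The documents give 7 instruments and 6 subdomains. Assume that executive function is one subdomain and that each instrument serves exactly one. The other 5 subdomains need at least 5 instruments, which leaves at most 7 − 5 = 2. Executive function then holds 1 or 2 of the 7.

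**Illustration of the consequence.** The plan gives no power figure to reproduce and no Toolbox weights, SDs, correlations or alpha. The 20 completers come from Description of Subject Population in the protocol. The rest is assumed: two-sided alpha 0.05, equal weights, correlation ρ between change scores of 0.1 to 0.3, and standardised change dz = 0.5 on each of m executive instruments and d_other on the rest. Power is from the noncentral t distribution with 19 degrees of freedom.

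- Total: dz = [(0.5m + (7 − m)·d_other)/7] / √[(1 + 6ρ)/7]
- Executive score: dz = 0.5 / √[(1 + (m − 1)ρ)/m]

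For m = 2, ρ = 0.1 and d_other = 0:
- Total: (1.0/7)/√(1.6/7) = 0.1429/0.4781 = 0.299
- Executive score: 0.5/√(1.1/2) = 0.674

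| Case | ρ | Total: dz (power) | Executive: dz (power) |
|---|---|---|---|
| Only 2 of 7 change | 0.1 | 0.299 (25%) | 0.674 (82%) |
| Only 2 of 7 change | 0.3 | 0.226 (16%) | 0.620 (75%) |
| Only 1 of 7 changes | 0.1 | 0.149 (10%) | 0.500 (56%) |
| Only 1 of 7 changes | 0.3 | 0.113 (8%) | 0.500 (56%) |

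If all 7 instruments change by 0.5, the total has dz = 0.5/0.4781 = 1.046 (99%) at ρ = 0.1 and 0.5/0.6325 = 0.791 (92%) at ρ = 0.3. It then has more power than the executive score.

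The two scores have equal power when the other instruments change by:
- 0.25 (ρ = 0.1) to 0.35 (ρ = 0.3) if m = 2
- 0.20 to 0.29 if m = 1

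**The responder contrast.** With 20 completers and a two-sample t-test, 80% power needs a between-group d of 1.32 (10 vs 10), 1.35 (12 vs 8) or 1.45 (14 vs 6). The paired test needs dz = 0.66. At a between-group d of 0.5, the responder contrast has about 19% power (10 vs 10) or 16% (14 vs 6).

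**The case against.** The strongest objection is that the total score is not the main obstacle. Hyp 2 is a between-group hypothesis, and the SAP drops the comparison, so Hyp 2 would go untested even with an ideal executive score. This is correct. It means that both elements must be repaired together; it does not make the total score a test of executive function.

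Second, the total fits Aim 2, the SAP's own second hypothesis and the protocol's general questions about cognitive deficits. This also stands: the total is a legitimate outcome for those. It does not alter what Hyp 2 predicts, and nothing says which statement governs.

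Third, the premise of 1 or 2 instruments is not in the documents. The protocol's account of NIH-EXAMINER treats executive functions broadly, so more Toolbox instruments might qualify. Under the same assumptions, with change in the executive instruments only, total-score power is 48% to 30% for 3 of 7 and 72% to 48% for 4 of 7. The executive score has 92% to 83% and 96% to 87%. The gap narrows but keeps its direction. The cases tabulated above are the severe end of an unknown range.

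Fourth, the paired-test figures do not describe the responder comparison that Hyp 2 calls for. That is right: they compare the two scores, and they do not show what the repaired Hyp 2 analysis would deliver at this sample size.

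**Conclusion.** The concern holds. The protocol's cognitive hypothesis has no matching analysis: the SAP substitutes a broader score and a different contrast, and no text reconciles them. This follows from the wording alone and needs no assumption.

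The size of the loss cannot be fixed from the documents. Under the stated assumptions it is large if change is concentrated in executive function, and it reverses if change is broad. The reason to correct the SAP is that it answers a different question, not that one score always has more power.

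This should be corrected before analysis. It concerns the second aim of a single-arm study that plans to enrol 25, and the total score remains a usable outcome.

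**What to change.** Amend the SAP before analysis in one of two ways.

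**To keep Hyp 2 as the protocol states it:**
1. Make its cognitive endpoint a prespecified Toolbox executive-function score. Name the instruments. If there is more than one, state how they are combined, for example by averaging after standardising each on its baseline mean and SD.
2. Keep the Toolbox total as a secondary outcome for Aim 2.
3. Define response, which neither document does. Compare change between responders and non-responders for the executive score and for gait speed, adjusted for baseline, as a difference with a 95% confidence interval. Keep the paired t-test as the within-subject analysis.

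**If the team intends overall cognition and within-subject change:** amend Hyp 2 to say so. This removes the inconsistency equally well.

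Analysing NIH-EXAMINER as well is optional. Baseline adjustment and the method of combining instruments are recommendations; the essential step is that the two documents agree.

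The cost is a few lines of text, since Toolbox testing is already planned. There are two downsides. A score from 1 or 2 instruments is less reliable than the total and has less power if change is broad (56%, or 82% to 75%, against 99% to 92% above). The responder contrast will be imprecise with 20 completers, so it is better read as an estimate with its interval than as a significance test.
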